California State Mental Health Services Act (MHSA)

American Academy of Child & Adolescent Psychiatry (AACAP)

Institutional Review Board (IRB)

Health Insurance Portability and Accountability Act (HIPAA)

SUMMARY

Background

Emotional dysregulation in justice-involved youth (JIY) is a condition that significantly impacts young people, their families, and juvenile justice and public health systems.

Affecting an estimated 60-70% of detained adolescents, it is a major driver of aggression, substance use, school failure, and later recidivism. Despite available treatments, managing emotional dysregulation in custody remains challenging, with youth often enduring high arousal, anger, and anxiety that persist into adulthood. Current therapies, including CBT and DBT, other therapy modalities such as EMDR, and brainspotting often fall short in detention because they rely on verbal processing, require multiple scheduled sessions, and need highly trained staff that facilities struggle to retain. Other newer technologies like neurofeedback, biofeedback and TMS are still under some scrutiny for adolescents given their Adverse Events (AEs) occurring at rates between 5-8% for neurofeedback/biofeedback and 10-12% for TMS. Recent research has highlighted sensory experiential therapy (like mindfulness, yoga, music, sound, vibroacoustics, light, journaling, etc.) can be a key mechanism in emotional regulation. For example, structured sound and music input, including gentle vibrations, can engage the autonomic nervous system to help reduce arousal. Notably, detention studies and pilots report that such brief non-verbal somatic, sensory, experiential sessions improve immediate regulation and therapy readiness, while a review of the broader literature shows increased heart-rate variability, reduced perceived stress, and better engagement after sound- and music-based sessions, underscoring the need for targeting these pathways.

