- TASC-R (Baseline + Midpoint + End).
- Structured journaling, therapist observations and validated scales with PHQ-9, GAD-7, and PSS-4 (every 2 weeks) will assess changes in coping strategies and mental health symptoms of depression, anxiety, and stress.
- Exploratory objectives will be addressed through qualitative analysis of journals and the feedback from therapists (by session) where applicable.
- Cognitive and behavioral coping will be evaluated with the standardized KidCOPE assessment tool (Baseline + Midpoint + End).

Key Design Features

- **Single-arm, open-label:** All participants will receive the intervention; no placebo or control group will be used.
- **Pre-post comparisons:** Each participant will serve as their own control, minimizing between-subject variability.
- **Setting:** The trial will be conducted at San Luis Obispo (SLO) County Juvenile Hall. All interventions will occur on-site.
- **Duration:** Each participant will be enrolled for 8 weeks, completing up to 16 Heal sessions plus baseline, bi-weekly, midpoint, and endpoint assessments.
- **Sample Size:** The study will enroll up to 8 participants (male and female youth ages 12-18).
- **Therapist involvement:** Facility therapists and/or probation staff will administer assessments and conduct post-session discussions to support integration of the intervention into therapy and be available for any AE support.

Rationale for Design

A randomized controlled trial (RCT) is not feasible in this setting due to the small population size of up to 18 juveniles in the SLO County Juvenile Hall. The pre-post design provides practical feasibility while still generating meaningful quantitative and qualitative data on changes in emotional regulation, therapeutic alliance, mental health outcomes, and coping. Findings from this pilot will inform the feasibility and effect sizes needed to plan a larger, fully powered RCT in the future.

Also, tracking emotional regulation not only with a dysregulation scale (e.g., DERS-16) but also with a mechanism-focused measure like MAIA will help us see if youths' body awareness/self-regulation improves. This lets us see *how* the Heal intervention might work, not just *if* it works.

Schedule of Assessments

Standardized Test	Start 0	Wk 1	Wk 2	Wk 3	Wk 4	Wk 5	Wk 6	Wk 7	Wk 8	
Mini-IPIP-A (Adolescent)	X									
MAIA-Y (Youth)	X				X					X
DERS-16	X				X					X
TASC-R	X				X					X
PHQ9	X		X		X		X			X
GAD7	X		X		X		X			X
PSS4	X		X		X		X			X
KidCope	X				X					X

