- **Parole board protections:** Adequate assurance has been established that participation in this research will not be considered by parole boards, probation officers, or other decision-making authorities when determining parole status, probation terms, or release dates. Participation or non-participation in the study will have no influence on legal outcomes, and this assurance will be communicated to both participants and their guardians during the consent/assent process.

Subpart D: Children and Minors in Research

Because participants are minors under 18, Subpart D applies. To ensure compliance with these regulations, this study is structured as follows:

- Parental/guardian/LAR consent will be obtained along with youth assent in age-appropriate language.
- The study involves minimal risk and offers a direct prospect of benefit through improved emotional regulation, improved therapeutic alliance, better mental health and improved coping skills.
- Youths with limited literacy will be supported by means of such assistance as non-guided/sounds-only sessions, journaling by drawing, and assisted prompts.
- Consent/assent documents will explicitly affirm the right to withdraw at any time without penalty.

Statistical Analysis

Study Purpose and Analytic Frame

This proposed research is a pilot, single-arm, pre-post interventional study with an expected enrollment of no more than 18 JIY detained in SLO County Juvenile Hall. The primary aim is to assess feasibility, safety, and preliminary signals of efficacy for the Heal intervention. Given the small sample size, analyses will emphasize within-person change estimates, effect sizes with confidence intervals, and graphical trajectories, rather than

confirmatory hypothesis testing. The data will provide estimates to inform a subsequent larger and adequately powered trial.

Variables and Endpoints

- **Primary outcome:** Emotional regulation, measured by the MAIA-Y, DERS-16 at baseline, mid-study, and study completion along with self-reported session journals.
- **Secondary outcomes:** Therapeutic alliance (TASC-R) measured at baseline, mid-point and end, and therapist assessment session journals. Mental health outcomes of depression (PHQ-9), anxiety (GAD-7), stress (PSS-4) measured every 2 weeks.
- **Exploratory outcomes:** Coping skills (KidCOPE) measured at baseline, mid-point and end, and study feasibility. Safety profile outcomes of AEs and SAEs.
-

Sample Size Rationale

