A target enrollment of no more than 18 participants reflects practical feasibility, given the facility population, expected length of stay, and consent requirement, and aligns with early-phase pilot norms. This sample is not designed to provide definitive efficacy testing; instead, it will yield effect-size estimates and variance parameters that will guide formal power calculations for a subsequent trial.

Primary Analyses

- **Primary endpoint (Emotional Regulation):**
Change in DERS-16 from Baseline to Week 8 will be the primary analysis.
- **Mechanism (Interoceptive Awareness):**
Change in MAIA-Y (Baseline, Week 4, Week 8) will be analyzed in parallel to test whether interoceptive awareness improves alongside DERS-16.
- **Therapeutic Alliance (Proximal clinical relevance):**
Change in TASC-R (Baseline to Week 4 to Week 8)

Secondary Analyses

- **Therapeutic alliance (detail):** Beyond the primary association analysis, report TASC-R domain-level changes (if scored) with paired tests and effect sizes.
- **Mental health symptoms: PHQ-9, GAD-7, PSS-4** (Baseline, Weeks 2/4/6/8).

Exploratory Analyses

- **Coping skills:** shifts in adaptive vs. maladaptive domains where applicable. KidCOPE scores (Baseline, Week 4, Week 8).

- Adverse events (AEs), and serious adverse events (SAEs): All AE's/SAE's will be documented and compiled into the analytic dataset. We will measure "counts and percentages" by event type (emotional, sensory, physical), severity (mild, moderate, severe), relatedness to the Heal intervention (unrelated / unlikely / possible / probable / definite) and expectedness (expected / unexpected)

Missing Data

Because some youth may be released, transferred, or choose to withdraw before completing the study, missing data are expected. To address this, this study will:

- **Use of all available data:** Analyses will include every data point that participants provide, even if they do not complete all sessions or the full 8-week period.
- **Handle incomplete cases:** If a participant is missing end-of-study data, their last available score will be carried forward as a sensitivity check to confirm whether results are consistent.
- **No complex imputation:** Given the small sample size, advanced statistical methods such as multiple imputation will not be used.
- **Transparency:** Results will be presented with clear notes about how many participants provided data at each timepoint, so that findings can be interpreted in light of attrition.

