Safety Monitoring Analysis

All AEs, SAEs, and Unanticipated Problems will be collected and documented. Because of the expected low event frequency, no inferential testing will be conducted for safety data. Any serious adverse events (SAEs) or unanticipated problems that arise will be reported.

Consent Process

Traditional Consent Process (Paper & Wet Ink)

- The person providing consent (parent/legal guardian/LAR) will be given as much time as they need to review study information and to make an informed decision.
- If more time is needed than the research timeline allows, the juvenile will not be enrolled.
- Probation/clinical staff at the SLO County Juvenile Hall will assess whether the parent/guardian/LAR or juvenile is under any pressure to decide quickly, and enrollment will not proceed if undue influence is suspected.
- No threat or adverse consequences will result if the parent/guardian/LAR declines participation.
- If the parent/guardian/LAR or juvenile indicates they do not wish to participate, the consent process will stop immediately.

- Probation/clinical staff will assess for coercion or undue influence by others and will not proceed if it is present.
- The consent process with the Junveniles will be conducted in age-appropriate basic level English.
- Presentation of the information will be adapted to the capacities of the parent/guardian/LAR and the juvenile in terms of intelligence, rationality, maturity, and language. The process will be culturally sensitive and be conducted in either basic level English or Spanish.
- All questions will be invited and answered.
- Probation/clinical staff will evaluate whether the parent/guardian/LAR and juvenile understand the study; if not, enrollment will not occur.
- No language will suggest waiving legal rights or releasing the sponsor/institution from liability.
- All the information in the consent document or script approved by the IRB will be communicated to the parent/guardian/LAR and the juvenile.
- The juvenile will not be enrolled if informed consent is not obtained.

Alternate Consent Process

Alternative approaches may be used if in-person paper consent is not feasible. Options include:

- **Asynchronous consent:** Parent/guardian/LAR may review consent forms online, discuss the study with research staff by phone or video, and then return signed forms via secure mail, email, or in person.

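### Safety is named in the primary aim, but the protocol fixes only counts and percentages by event class, with no participant denominator and no stated precision; zero affected youths would exclude only risks above 18.5% (n=18) or 36.9% (n=8).

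*Protocol*

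**What the plan says.** **Rank of safety.** Statistical Analysis, Study Purpose and Analytic Frame: "The primary aim is to assess feasibility, safety, and preliminary signals of efficacy for the Heal intervention". The next subsection, Variables and Endpoints, puts the same material under exploratory outcomes: "Safety profile outcomes of AEs and SAEs". The Summary's objectives and the Exploratory Analyses subsection also treat adverse events (AEs) and serious adverse events as exploratory.

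**Planned summary.** Exploratory Analyses plans counts and percentages "by event type (emotional, sensory, physical), severity (mild, moderate, severe"), and then by relatedness and expectedness. It does not say whether the percentages are of youths, of sessions or of events.

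**Inference.** Safety Monitoring Analysis: "Because of the expected low event frequency, no inferential testing will be conducted for safety data". It mentions tests only; intervals are neither planned nor excluded.

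**General approach.** The Analytic Frame says that "analyses will emphasize within-person change estimates, effect sizes with confidence intervals, and graphical trajectories, rather than" confirmatory testing. It does not say whether this covers event proportions.

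**Sample size.** Key Design Features: "The study will enroll up to 8 participants". The Analytic Frame and Sample Size Rationale give a maximum of 18.

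**Relatedness.** Safety Plan, Definitions, has three levels (unrelated, possibly related, definitely related). Exploratory Analyses has five (unrelated, unlikely, possible, probable, definite).

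**The concern.** Safety is one of three things the trial is said to be for, and the data are meant to supply estimates for a larger trial. A table of events by class does not answer the basic question of how many of the youths were affected. With 8 to 18 participants, a bare small percentage or a bare zero carries almost no information unless its uncertainty is shown beside it.

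The protocol itself shows how a bare zero can be over-read. The Introduction, the Justification and Risk Mitigation rest the safety case on the adult program: no events in 105 adults and about 1,117 sessions, with no upper limit given. The Justification takes this as a well-characterized safety profile, and Risk Mitigation uses it to support the minimal-risk classification. A zero from this pilot could be carried into the next protocol in the same way.

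**Working it through.** The protocol states no safety precision, detectable event rate or confidence level, so there is no figure to reproduce. The 95% level is an assumption.

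**Inputs.** n = 8 (Key Design Features) or n = 18 (Sample Size Rationale); up to 16 sessions per youth (Intervention Arm); adult experience of 0 events in 105 people and about 1,117 sessions (Introduction). The unit is the youth.

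**1. Upper limit with zero affected youths.** The exact (Clopper-Pearson) two-sided 95% limit is 1 − 0.025^(1/n); the one-sided limit is 1 − 0.05^(1/n).

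| n | Two-sided exact | One-sided exact | Wilson |
|---|---|---|---|
| 8 | 1 − 0.025^(1/8) = 36.9% | 31.2% | 32.4% |
| 18 | 1 − 0.025^(1/18) = 18.5% | 15.3% | 17.6% |

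The choice of method matters little. The choice between 8 and 18 doubles the exact bound (36.9/18.5 ≈ 2.0).

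**2. One or two affected youths.** Zero is not the only imprecise result. The exact 95% intervals are:
- 1 of 8 (12.5%): 0.3% to 52.7%; 2 of 8 (25.0%): 3.2% to 65.1%
- 1 of 18 (5.6%): 0.1% to 27.3%; 2 of 18 (11.1%): 1.4% to 34.7%

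**3. Chance of seeing no affected youth at a true per-youth risk p**, which is (1 − p)^n:

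| p | n = 8 | n = 18 |
|---|---|---|
| 5% | 66% | 40% |
| 8% | 51% | 22% |
| 10% | 43% | 15% |
| 12% | 36% | 10% |

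These values of p span the rates in the Summary's Background, "Adverse Events (AEs) occurring at rates between 5-8% for neurofeedback/biofeedback and 10-12% for TMS". Using them here **assumes that they are per-person rates**; the protocol gives no unit. The Introduction also gives a different TMS range, 3.42% to 5.97%. All of these rates lie below the upper limits in step 1, so zero affected youths would exclude none of them.

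**4. Why the denominator must be stated.** The most sessions possible are 8 × 16 = 128 or 18 × 16 = 288. If sessions were treated as independent, the same formula for zero events would give 1 − 0.025^(1/128) = 2.8% or 1 − 0.025^(1/288) = 1.3% per session. The per-youth limits are 36.9% and 18.5%. These are different quantities, and the session figures are too narrow as well, because repeated sessions in one youth are not independent. The adult data show the same contrast: 0 of 105 people gives 3.5%, while 0 of 1,117 sessions gives 0.33%.

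**The case against.** The strongest reply is that nothing in the text is wrong. Much of that stands.

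- **Intervals are not ruled out.** A reader might infer that the protocol omits them because events are rare, and that this reasoning is backwards. The sentence does not say so. Low frequency is given as the reason for not testing, and with no comparator that is sound.
- **The statistical analysis plan may supply intervals.** The protocol refers to such a plan, which is not shown, and exact limits and table denominators are often left to it. Their absence here is therefore not an error in itself. What can be judged is the summary that the protocol does fix.
- **No comparison with other technologies is planned.** A reader might infer that a zero will be presented as safer than neurofeedback or TMS. The protocol gives those rates as background, without a unit, and predicts no such claim. Step 3 is illustrative only.
- **Zero AEs of any kind is not the obvious result.** The AE definition covers unrelated events, the listed examples include emotional upset and refusal to continue, and mild transient responses are expected. A zero is more plausible for related or serious events, which is why related AEs need their own line. Step 2 shows that a count of one or two is hardly more precise.
- **Safety is also ranked exploratory.** This weakens any argument built only on the primary-aim sentence. It is also a contradiction that the protocol should resolve.

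What the reply does not remove is that the protocol commits to estimates with confidence intervals as its general approach, names safety in its aim, and then specifies for safety a summary with neither a person-level proportion nor a measure of its uncertainty.

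**Conclusion.** The point holds as a minor improvement, not as an error of method. The decision not to test AEs should stay. The planned safety summary is too thin for something named in the primary aim, because the fraction of youths affected, and how well it is known, are not stated. At two-sided 95% confidence, zero affected youths would exclude only per-youth risks above 36.9% (n=8) or 18.5% (n=18). These limits assume that every enrolled youth counts in the denominator and that youths are independent; fewer evaluable youths would widen them. The limits do not depend on the Summary's comparison rates; any remark about those rates rests on the per-person assumption.

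**What to change.** In Exploratory Analyses and Safety Monitoring Analysis:

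1. Keep the statement that no hypothesis tests will be done on safety data.
2. Add the number and percentage of participants with at least one AE, and with at least one intervention-related AE, each with an exact (Clopper-Pearson) 95% confidence interval. Keep the event counts by class alongside.
3. Report events per session delivered, with the Healpod session log as denominator, descriptively and without an interval that treats sessions as independent.
4. State in advance which per-youth risks zero affected youths would exclude at the final sample size.
5. First reconcile three things on which these lines depend: the sample size (8 in Key Design Features, 18 in Statistical Analysis), the rank of safety (primary aim or exploratory), and the relatedness scale (three levels or five), since the related-AE line cannot be defined until one scale is used.
6. If the Background rates are ever set beside this trial's results, state that a per-person unit is assumed.

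The cost is a few lines of text and two extra rows of output, with no new data collection. The downside is that the safety statement becomes less favourable.
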